11.4 Resistance Analysis

Genotypic and phenotypic assessment will be conducted to determine the emergence of VIS410-resistant viruses. Sample selection for genotypic testing will be based on primary virology qPCR data. Phenotypic analysis will be performed based on the genotypic analysis. Results will be summarized in a genotypic report and a phenotypic report.

11.5 Exploratory Pharmacokinetic/Pharmacodynamic Analyses

Associations between serum VIS410 PK exposure parameters (AUC, C_{max}) with virology endpoints will be evaluated. The dependent variables (endpoints) which will be explored in this analysis will be:

- Viral Load AUC (TCID₅₀ and qRT-PCR)
- Peak Viral Load (TCID₅₀, qRT-PCR)
- Duration of viral shedding (TCID₅₀, qRT-PCR)

The independent variables (PK exposure parameters) will include serum VIS410 AUC and C_{max}. Univariable analyses will be conducted to explore the relationship between independent variables and dependent, as summarized above. Various techniques will be used to explore exposure-response relationships. These techniques may include graphical and statistical methods, including the creation of boxplots, spaghetti plots, histograms, and a variety of linear, nonlinear, or logistic regression techniques and time-to-event methods, as appropriate. Decisions with regards to methods used will be based on the nature of the data, and strengths of relationships identified via graphical evaluation. If appropriate, continuous independent variables will be evaluated as such, and also as categorical variables (grouping subjects into exposure categories). Categories based on subject groupings will include quartiles, but also the implementation of

Classification and Regression Tree Analysis (CART) to identify significant target breakpoints. Results of the exploratory analyses may be reported in the clinical study report, or may be reported separately.

11.6 Anti-drug Antibodies

Anti-VIS410 antibody titer will be summarized by treatment group and time point using descriptive statistics.

12 SAFETY ANALYSES

All safety analysis will be carried out using the safety population and the subject's actual treatment received.

12.1 Adverse Events

A TEAE is defined as an adverse event that starts on or after the date of study drug IV infusion. AEs that start on the day of infusion will be classified as TEAEs if the "Same day as infusion" question is answered as "Started after the infusion." All AEs will be coded using MedDRA version 19.1.

An overall summary of AEs and TEAEs will be presented by treatment group, including the combined low-dose and high-dose VIS410, and overall subjects, with subject counts, percentages, and the exact 95% CI for the percentage of subjects with the event. This summary will include subjects with any AE, any treatment-related AE, any TEAE, any treatment-related TEAE, any serious TEAE, any treatment-related serious TEAE, any TEAE of special interest (AESI), hypersensitivity reaction, anaphylactic reaction, any injection site AE, TEAEs by intensity, any moderate TEAE, any severe TEAE, TEAEs leading to study infusion discontinuation, treatment-related TEAEs leading to study infusion discontinuation, TEAEs leading to death, and treatment-related TEAEs leading to death.

TEAE definitions:

- All AESIs will be defined by the eCRF field event type - AESI
- Injection site AEs will be defined by the eCRF field event type - injection site AE
- Treatment related AEs will be defined by the investigators determination of the relationship as a reasonable possibility.
- Hypersensitivity and anaphylaxis reactions will be defined by clinical evaluation of TEAEs per the Safety Plan
- TEAEs leading to study infusion discontinuation will be defined by an answer of permanently discontinued as the eCRF action taken for an AE during infusion.

This summary will also be presented by region: US, Africa, Rest of the World.

A summary table by treatment group will present the number and percentage of subjects with TEAEs by SOC and SOC/PT. Subjects with multiple TEAEs within an SOC or SOC/PT combination will be counted only once for that SOC or SOC/PT combination. This table will also present a summary of subjects with any TEAE.

Similar summaries will be presented for Serious TEAEs, AESIs, injection site TEAEs, treatment-related TEAEs, TEAEs leading to study infusion discontinuation and TEAEs leading to death. The TEAE definitions for these tables will be the same as used in the overall summary of TEAEs.

A summary table by treatment group will be presented summarizing the intensity (mild, moderate, or severe) associated with each SOC and SOC/PT. A subject will be counted only once for an SOC or an SOC/PT combination. If a subject experiences multiple events in the same SOC or SOC/PT the highest recorded intensity will contribute counts to the summary table.

A summary table, by treatment group, will be presented for the TEAE relationship (reasonable possibility or no reasonable possibility) associated with each SOC and SOC/PT. A subject will be counted only once for an SOC or an SOC/PT combination. If a subject experiences multiple events in the same SOC or SOC/PT the closest relationship to study drug will contribute counts to the summary table.

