9.3.8 Safety

The ITT, and safety populations will be used for the safety summaries. Additional populations may be analyzed and this will be documented in the SAP.

Adverse Events

The original terms in the EDC system by Investigators to identify AEs other than symptoms of influenza A will be fully described and coded according to the Medical Dictionary for Regulatory Activities (MedDRA current version 19). The reported AEs will be allocated to phases based on their start date. All AEs will be listed. All AEs with onset during the treatment phase (TEAEs) will be summarized.

AEs will be summarized by treatment group and by MedDRA body organ system and preferred term, severity, relatedness, and seriousness. Classical symptoms of influenza including cough, sore throat, nasal congestion, fatigue, headache, myalgia or low-grade fever should not be reported as AEs unless there is a relationship between the event and study medication.

The difference in proportions of subjects with AEs, TEAEs, AESIs, and SAEs between treatment groups and their 95% CI will be calculated (primary safety endpoint).

Special attention will be paid to those subjects who died, discontinued the study drug due to an AE, or experienced a severe or serious AE. Summaries, listings, and narratives (also see Section 12.11) may be provided, as appropriate.

Injection Site Tolerability

Injection site tolerability is defined as AEs demonstrating significant injection site irritation or tissue damage. Injection site tolerability will be reported by variable, treatment group, and time point.

Complications of Influenza

Complications of influenza are defined as pneumonia, myocarditis, worsening of chronic bronchitis, other chronic pulmonary diseases, otitis, sinusitis, and death. Complications of influenza will be reported by variable, treatment group, and time point.

Clinical Laboratory Tests

Actual values and changes from baseline of each continuous biochemistry, hematology and urinalysis test will be evaluated using descriptive statistics by assessment time point and by treatment group. For categorical urinalysis tests, frequency tables of actual values will be provided by assessment time point and by treatment group.

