10. ADVERSE EVENT REPORTING

10.1 DEFINITIONS

Type of Event	Collection Period
AESIs ^a	28 days after drug administration
TEAEs	Entire study period ^b
SAEs ^c and Pregnancies	Entire study period ^{b, d}

^a If a subject was enrolled with a concurrent AESI, received investigational product, and then has worsening of an AESI (severity of symptoms), then this event should also be reported.

^b The entire study period is from the time a subject receives the study drug through the Day 100 Visit.

^c If the Investigator becomes aware of any related SAE after completion of the study, he or she is obligated to report this event.

^d If a subject or the female partner of a male subject, becomes pregnant during the study or within 100 days following study drug infusion, the Sponsor must be notified within 24 hours of the site's knowledge of the pregnancy; the subject or partner will be followed until the end of the pregnancy; and the infant will be followed for 1 year after the birth, provided informed consent is obtained.

Adverse Event

An AE is any untoward medical occurrence in a patient administered a medicinal (investigational or non-investigational) product in a clinical study. An AE does not necessarily have a causal relationship with the treatment. An AE can therefore be any unfavorable and unintended sign (including an abnormal finding), symptom, or disease temporally associated with the use of a medicinal (investigational or non-investigational) product, whether or not related to that medicinal (investigational or non-investigational) product.

This includes any occurrence that is new in onset or aggravated in severity or frequency from the baseline condition, or abnormal results of diagnostic procedures, including clinical laboratory test abnormalities.

New or worsening symptoms of influenza including cough, sore throat, nasal congestion, fatigue, headache, myalgia or low-grade fever should not be reported as AEs unless they result in an SAE (i.e., lead to hospitalization).

Adverse Event of Special Interest

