The Sponsor or designee will report SUSARs and other applicable SAEs to the appropriate regulatory authorities, Central Institutional Review Board (IRBs)/Ethics Committees (ECs) and Investigators as required, according to local law.

Treatment-Emergent Adverse Event

A TEAE is defined as any event not present prior to the initiation of the treatments or any event already present that worsens in either intensity or frequency following exposure to the treatments.

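### SAP 12.1 defines a treatment-emergent AE more narrowly than protocol 10.1: no worsening limb, no default for a Day 1 event without an eCRF answer, and no stated start-of-infusion cut (minor)

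*SAP*

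**What the plan says.** Three places define a TEAE.

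- **SAP 12.1** begins: "A TEAE is defined as an adverse event that starts on or after the date of study drug IV infusion". It then adds that events starting on the infusion day are "classified as TEAEs if the 'Same day as infusion' question is answered as 'Started after the infusion". It does not mention worsening of an event already present.
- **Protocol 10.1** counts "any event not present prior to the initiation of the treatments or any event already present that worsens in either intensity or frequency" after exposure.
- **Protocol 9.3.8** allocates events to phases by start date and says: "All AEs with onset during the treatment phase (TEAEs) will be summarized".

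Other text bears on the reading. Protocol 10.1 defines an AE to include "any occurrence that is new in onset or aggravated in severity or frequency from the baseline condition". Note a to its collection-period table asks for a concurrent AE of special interest (AESI) that worsens after dosing to be reported as well. Note b starts the TEAE collection period when the subject receives study drug. SAP 4.2 imputes certain partial onset dates to the dosing day, under a stated policy of maximum conservatism. SAP 16.1 declares three changes from the protocol (Day 14 ADA, viral-load sampling, QTcF categories) and nothing on TEAEs.

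SAP 2.3 evaluates treatment differences through exact confidence intervals on TEAE incidence. SAP 3.1 makes the proportion with TEAEs, including hypersensitivity and anaphylactic reactions, a primary endpoint.

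**The concern.** The SAP rule is the one that will be programmed, and on its face it captures less than the protocol's own definition of a primary-endpoint event. There are three possible losses.

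1. **Worsening.** A pre-existing event that gets worse after dosing, but is kept as one record with a pre-dose start date, is a TEAE under protocol 10.1 and not under SAP 12.1.
2. **No answer.** An event whose partial date is imputed to the dosing day falls under the same-day rule. If the same-day question is blank, the condition in that rule is not met.
3. **Onset during infusion.** The infusion lasts 2 hours and may be extended to 4 (protocol 5.4). The SAP does not say whether the same-day answer refers to its start or its end.

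An event lost in any of these ways could leave the any-TEAE, serious, intensity and SOC/PT outputs. It could also leave the hypersensitivity outputs, because "Hypersensitivity and anaphylaxis reactions will be defined by clinical evaluation of TEAEs per the Safety Plan". The AESI row is less clear, because it also has its own rule: "All AESIs will be defined by the eCRF field event type - AESI". Affected events would remain in the any-AE row, which also reports a primary endpoint, in the listing, and in the any treatment-related AE row if judged related.

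**Working it through.** The plan states no figure to reproduce. The check compares the texts and then gives an order of magnitude.

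**Step 1: worsening.** Protocol 10.1 includes it; protocol 9.3.8 and SAP 12.1 do not. So two onset rules stand against one wider definition, and the inconsistency is already inside the protocol. The AE definition in 10.1 narrows the gap: an aggravation entered as a new record with its own post-dose start date is a TEAE under all three texts. No text in either document requires a new record, so the loss is confined to worsening held under a pre-dose start date. Such records can exist, because AEs are recorded from signing of consent (protocol 7.6.1).

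**Step 2: same-day event without an answer.** Under SAP 4.2, an onset with the day missing, in the month of dosing, is imputed to the dosing date. That satisfies the first sentence of SAP 12.1. The second sentence does something only if it restricts the first, and then a blank answer means not treatment-emergent. That runs against the conservatism stated in SAP 4.2. By contrast, SAP 7 gives a default for medications: one that cannot be confirmed as stopped before the start of infusion is classed as both prior and concomitant. The AE rule has no such default.

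**Step 3: start or end of infusion.** These texts favour the start:
- protocol 10.1, which refers to initiation of treatment, and its note b;
- SAP 7, which uses the start of infusion for medications;
- the first sentence of SAP 12.1;
- SAP 12.1 on TEAEs leading to infusion discontinuation, which "will be defined by an answer of permanently discontinued as the eCRF action taken for an AE during infusion". If events during infusion were not TEAEs, that row would be nearly empty.

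Only the ordinary sense of the answer wording points to the end. SAP 11.3 shows that the SAP names the end of infusion when it means it.

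**Step 4: size, onset during infusion (illustration).** Inputs are the VIS410-102 groups pretreated with diphenhydramine plus ibuprofen or acetylsalicylic acid (protocol 1.3), with exact 95% CIs. The subject who stopped the infusion is taken as a third 3800 mg subject.
- GI events: 2/12 + 1/11 + 3/12 = 6/35 = 17.1% (6.6 to 33.6).
- Four of the six began about 7 to 22 hours after infusion start, so they are TEAEs on either reading.
- Without the subject who stopped the infusion: 5/35 = 14.3% (4.8 to 30.3).
- Also without the one mild nausea that has no onset time: 4/35 = 11.4% (3.2 to 26.7).
- Shift: 1/35 = 2.9% to 2/35 = 5.7%. With 150 × 2/3 = 100 VIS410 subjects, that is about 3 to 6.
- For comparison, 17/100 has an exact CI of 10.2 to 25.8.

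This range is weak. The lower figure is the type of case that SAP 12.1 itself treats as a TEAE in its discontinuation row, and the upper figure adds an event of unknown timing. Both assume that the removed subjects had no other TEAE.

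**Step 5: size, worsening (illustration).** The documents give no count. Take 8/50 = 16% (7.2 to 29.1) in one arm. If 1, 3 or 5 further subjects qualify only through worsening, the result is 9/50 = 18% (8.6 to 31.4), 11/50 = 22% (11.5 to 36.0) or 13/50 = 26% (14.6 to 40.3).

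**The case against.** The strongest reply is that this is a missing clarification. The rule quotes an eCRF answer whose alternatives are not shown. If the only alternative is before the infusion, the start/end question disappears, and the context in step 3 already answers it. The SAP follows protocol 9.3.8, the protocol's statistical section, so it is arguable that SAP 16.1 had nothing to declare. Worsening is largely handled by the AE definition and by the AESI note. Influenza symptoms are generally not AEs, and screening and baseline may fall on the same day, so few pre-dose events could worsen. Missing answers can be queried in routine data cleaning (protocol 12.6). Many affected subjects would probably have another TEAE over 100 days: in Phase 1, 20/30 on VIS410 and 7/11 on placebo did.

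Most of this stands, and it limits the severity. It does not remove the gap. The SAP never states the cut, gives no default when a query stays unanswered, and omits a limb that protocol 10.1 includes.

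A reader might infer more in four ways that the documents do not support.

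- **That the SAP excludes reactions during the infusion from TEAEs.** The weight of the text is the other way, and the eCRF is not available.
- **That three definitions all disagree on worsening.** Two share an onset rule and one adds worsening.
- **That SAP 16.1 declares no changes.** It declares three; it is silent only on this one.
- **That the rule would favour VIS410.** In the first VIS410-201 cohort, 6 of 7 VIS410 and 0 of 5 placebo subjects had cramping, loose stool and/or diarrhea, mostly during infusion or within 30 minutes of its end. That cohort had no pretreatment and the two periods are not separated. Placebo subjects can also have events during infusion, so the direction is plausible but not established.

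**Conclusion.** The point holds as a minor one. Read literally, SAP 12.1 is narrower than the TEAE definition in protocol 10.1 on a primary endpoint. The firm part is the missing worsening limb and the missing default for a same-day event with an imputed date and no answer. The start/end question is a clarification, with the context favouring the start. The size in this trial is unknown, because neither the eCRF options nor the number of worsened pre-dose events is given. It is probably small: the only illustration available moves a GI rate by 2.9 to 5.7 percentage points, less than the width of its own confidence interval, and rests on two subjects whose relevance is doubtful.

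**What to change.** Before unblinding, amend SAP 12.1 as follows.

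- Define a TEAE as an AE with onset at or after the start of study drug infusion, or a pre-existing event that worsens in intensity or frequency after that start.
- Class a same-day AE as not treatment-emergent only if it is recorded as starting before the start of infusion.
- Count same-day AEs with a missing answer or an imputed date as TEAEs.
- State how each eCRF answer maps to TEAE status. If one option means after the end of infusion, resolve the remaining same-day events by query, or by recorded times if these are collected.
- State how worsening of a pre-dose event is recorded, so that the second limb can be programmed.
- Bring protocol 9.3.8, protocol 10.1 and SAP 12.1 into line. If the narrower rule is kept, declare it in SAP 16.1 as following 9.3.8 and not 10.1.

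The cost is a few sentences, one derivation rule and possibly a few data queries. TEAE rates may come out slightly higher.

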1.3 CLINICAL STUDIES

Phase 1 (VIS-C001). In a Phase 1 study (VIS-C001), a total of 30 healthy volunteers received a single, 120-minute IV infusion of 2, 5, 15, 30, or 50 mg/kg of VIS410 (200 mL volume) (6 subjects per cohort) and 11 subjects received a single, 120-minute IV infusion of placebo (sodium chloride 0.9%; 200 mL volume).

The PK and safety data are presented below.

Pharmacokinetics

PK profiles of the serum and nasopharyngeal samples demonstrated that VIS410 exposure was approximately proportional to the dose administered with a mean serum $t_{1/2}$ of 12.9 days. This $t_{1/2}$ is within the expected range for the IgG1 molecules. In addition, the 13-day $t_{1/2}$

supports the single dosing of VIS410, as the circulating levels should be sufficiently high during the normal course of an influenza infection in hospitalized patients (5–14 days). The maximum concentration (C_{\max}) values in the serum for the 30 and 50 mg/kg cohorts were 980 and 1316 $\mu\text{g/mL}$, respectively.

Nasopharyngeal swabs were taken from the 15, 30, and 50 mg/kg cohorts for upper respiratory pharmacokinetics. The nasopharyngeal PK profiles were approximately dose proportional. Mean nasal C_{\max} values at the 30 and 50 mg/kg dose levels were 20.0 and 25.3 $\mu\text{g/mL}$, respectively.

Safety

Overall, VIS410 was generally safe and well tolerated at all dose levels studied. Treatment-emergent adverse events (TEAEs) were reported for 20/30 (66.7%) subjects receiving VIS410 and 7/11 (63.6%) subjects receiving placebo. There were no drug-related serious adverse events (SAEs), no drug-related discontinuations, and no infusion-related reactions such as anaphylaxis or injection site reactions.

Notable adverse events (AEs) included one unrelated SAE of leukopenia and esophagitis secondary to primary HSV-1 infection in one subject (VIS410, 30 mg/kg cohort). This SAE resolved and the subject is doing well. Another unrelated SAE of acute appendicitis was also reported (placebo cohort).

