The most common AEs observed were diarrhea (10/41, 24.4%) and headache (8/41, 19.5%). All diarrheal or loose stool AEs were observed in the VIS410-treated subjects and were usually mild to moderate, started ~2–4 hours after dosing, were transient and resolved spontaneously within 24 hours after dosing with no associated dehydration. The gastrointestinal (GI) events were dose proportional and the majority of the AEs were observed at the highest dose tested (50 mg/kg). None of the GI events were associated with a systemic allergic reaction or elevation in liver or biliary laboratory values. Mean hematology, serum chemistry, and urinalysis results were within the normal limits and the mean values and changes from baseline were similar across the treatment groups and placebo. Overall, mean vital sign measurements observed after dosing were similar to those observed at baseline. Mean changes from baseline were also similar across VIS410 dose levels, and no apparent treatment- or dose-related trends were observed.

The anti-drug antibody (ADA) data demonstrated a low level of positive ADA in 4 out of 30 subjects receiving VIS410 (Table 2). The subjects with positive ADA did not demonstrate any impact on their PK profile.

Table 2. Study VIS-C001 ADA Data

Cohort Dose (mg/kg)	No. of Confirmed ADA Positive	Pre-Infusion Titer	Confirmed Day	Positive Titer
2	0/6	None detected	NA	None detected
5	3/6	None detected	120	titer 10
		None detected	14	titer 10
		None detected	120	titer 40
		None detected	120	titer 40
15	1/6	None detected	120	titer 40
30	0/6	None detected	NA	None detected
50	0/6	None detected	NA	None detected

Phase 2a Challenge Study (VIS410-201). Study VIS410-201, “A Phase 2a Randomized, Double-blind, Placebo-controlled Study to Assess the Safety, Tolerability and Antiviral Activity of a Single Intravenous Dose of VIS410 in Healthy Subjects after a Viral Inoculation with Influenza A (H1N1),” was conducted at a single site in Antwerpen, Belgium by SGS Life Sciences. Briefly, 24 hours after inoculation with a 10^6 tissue culture infective dose (TCID) of naturally attenuated influenza A (H1N1) virus [7], subjects receive a single IV administration of VIS410 (2300 mg fixed dose, equivalent of 30 mg/kg) or placebo (7:5 randomization to VIS410:placebo). Subjects were quarantined 10 days post-inoculation and discharged thereafter.

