2.3 Primary Hypothesis

The primary objective is to assess the safety and tolerability of a single IV dose of VIS410 in subjects with uncomplicated influenza infection. There is no formal statistical testing for this protocol; differences between the treatments will be evaluated with 95% exact confidence intervals (CI) of the incidences of treatment-emergent AEs (TEAEs).

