16 APPENDICIES

16.1 Changes to the Protocol Specified analyses

ADA data at Day 14 will not be analyzed.

Nasopharyngeal viral load samples will only be analyzed for qPCR and TCID₅₀ until Day 7, unless still positive on Day 7, and then samples will also be analyzed on Day 14. No PCR or TCID₅₀ samples are planned to be analyzed post-Day 14.

QTcF interval prolongation categories were updated to <450, >450 to ≤480, >480 to ≤500, and >500 msec and categories for QTcF increases were updated to <30, >30 to ≤60 and >60 msec from Baseline.

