14.2.1.8A	Summary of FluPRO Area Under the Curve for Domain Scores, Component Scores, and Total Score by Mean- Excluding Subjects Who Received Antiviral Therapy in First 10 days of Study	mITT
14.2.1.8B	Summary of FluPRO Area Under the Curve for Domain Scores, Component Scores, and Total Score by Sum – Excluding Subjects Who Received Antiviral Therapy in First 10 days of Study	mITT
14.2.2.1	Summary of Oral Temperature Patient Diary Data	mITT
14.2.2.2	Kaplan-Meier Estimates of Median Time to Normal Temperatures	mITT
14.2.2.3	Influenza Symptom Complications	mITT
14.2.2.4	Summary of Hospitalizations	mITT
14.2.2.5	Summary of Influenza A Relapse	mITT
14.3.1.1	Overall Summary of Adverse Events	Safety
14.3.1.2	Overall Summary of Adverse Events by Region	Safety
14.3.1.3	Summary of Treatment Emergent Adverse Events	Safety
14.3.1.4	Summary of Treatment Emergent Adverse Events Occurring in $\geq 5\%$ of Subjects in Any Treatment Group	Safety
14.3.1.5	Summary of Serious Treatment Emergent Adverse Events	Safety
14.3.1.6	Summary of Treatment Emergent Adverse Events of Special Interest	Safety
14.3.1.7	Summary of Injection Site Adverse Events	Safety
14.3.1.8	Summary of Treatment-Related Treatment Emergent Adverse Events	Safety
14.3.1.9	Summary of Treatment Emergent Adverse Events Leading to Infusion Discontinuation	Safety
14.3.1.10	Summary of Treatment Emergent Adverse Events Leading to Death	Safety
14.3.1.11	Summary of Treatment Emergent Adverse Events by Relationship	Safety
14.3.1.12	Summary of Treatment Emergent Adverse Events by Intensity	Safety
14.3.5.1	Hematology - Summary and Change from Baseline	Safety
14.3.5.2	Hematology – Values Compared to Normal Range (Low, Normal, High)	Safety
14.3.5.3	Hematology – Shift Tables by Microbiology and Infectious Diseases (DMID) Grades	Safety
14.3.5.4	Chemistry and Coagulation - Summary and Change from	Safety

Table	Title	Population
	Baseline	
14.3.5.5	Chemistry and Coagulation – Values Compared to Normal Range (Low, Normal, High)	Safety
14.3.5.6	Chemistry and Coagulation – Shift Tables by Microbiology and Infectious Diseases (DMID) Grades	Safety
14.3.5.7	Urinalysis - Summary and Change from Baseline	Safety
14.3.5.8	Urinalysis – Categorical Parameter Summaries	Safety
14.3.5.9	Urinalysis – Shift Tables of Categorical Summaries	Safety
14.3.5.10	Vital Signs - Summary and Change from Baseline	Safety
14.3.5.11	Vital Signs – Summary of Not Done, Normal, Abnormal, and Clinically Significant	Safety

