16.7 Tables, Figures, and Listings Shells

Table shells are in a separate document. Shells will be completed after the SAP text is finalized.

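### The SAP does not specify the protocol's primary safety contrast (95% CI for the between-group difference in AE proportions), and SAP 16.1 does not declare the change

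*SAP*

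**What the plan says.** Protocol 9.3.8 states: "The difference in proportions of subjects with AEs, TEAEs, AESIs, and SAEs between treatment groups and their 95% CI will be calculated (primary safety endpoint"). The synopsis says the same. Protocol 9.3 sets the contrasts: VIS410 pooled, and each dose level, against placebo.

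The SAP treats the same data differently:

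- SAP 2.3 rules out formal testing and says "differences between the treatments will be evaluated with 95% exact confidence intervals (CI) of the incidences of treatment-emergent AEs (TEAEs").
- SAP 12.1 specifies an overall summary by treatment group, including combined VIS410, "with subject counts, percentages, and the exact 95% CI for the percentage of subjects with the event". It names no difference, contrast or method for a difference interval.
- SAP 16.6.1 lists Tables 14.3.1.1 to 14.3.1.12 for adverse events. The first is titled "Overall Summary of Adverse Events". No title in the set refers to a difference or a comparison.
- SAP 16.1, which records departures from the protocol's analyses, has three entries: "ADA data at Day 14 will not be analyzed", a restriction on viral load samples, and revised QTcF categories. The adverse event analysis is not among them.

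**The concern.** The trial has no formal test and no sample size calculation, so estimation of the adverse event contrast is the whole of its primary analysis. The endpoint itself, the proportion of subjects with events, is kept in the SAP. What has gone is the planned contrast with placebo and the interval that shows how precisely it is estimated.

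Two intervals, one per group, do not give the precision of their difference. A reader left to compare them by eye will tend to judge by overlap, which understates the evidence for a moderate excess of events.

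Disclosure is also at stake. SAP 4.1 requires the study report to document deviations from the SAP. An analyst who follows the SAP has not deviated from it, so neither that rule nor 16.1 would bring the missing analysis to light.

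**Working it through.** **Step 1: the text, side by side**

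| | Protocol synopsis and 9.3.8 | SAP 2.3 and 12.1 |
|---|---|---|
| Quantity | Difference between groups | Percentage in each group |
| Interval | 95% CI of the difference, method not named | Exact 95% CI of each percentage |
| Events | AEs, TEAEs, AESIs, SAEs | 2.3: TEAEs only; 12.1: a longer list, with serious TEAEs rather than SAEs |
| Contrasts | Pooled VIS410 and each dose against placebo (9.3) | None named |
| Declared in 16.1 | – | No |

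Neither document gives a precision figure to reproduce. The rest of the check asks whether the SAP's output can stand in for the protocol's.

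**Step 2: the documents' own data**

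Protocol 1.3 reports diarrhea in 10 of 41 subjects in the Phase 1 study VIS-C001, where 30 received VIS410 and "11 subjects received a single, 120-minute IV infusion of placebo". It adds: "All diarrheal or loose stool AEs were observed in the VIS410-treated subjects". That gives 10/30 against 0/11.

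- SAP method (Clopper-Pearson): 17.3 to 52.8% on VIS410 and 0 to 28.5% on placebo. The intervals overlap, since 17.3 < 28.5.
- Protocol quantity: d = 10/30 − 0/11 = 0.333. For the Newcombe interval, the Wilson limits are 0.1923 to 0.5122 (VIS410) and 0 to 0.2588 (placebo).
  - Lower limit = d − √[(p₁ − l₁)² + (u₀ − p₀)²] = 0.3333 − √(0.1410² + 0.2588²) = 0.3333 − 0.2948 = 0.039.
  - Upper limit = d + √[(u₁ − p₁)² + (p₀ − l₀)²] = 0.3333 + √(0.1789² + 0²) = 0.512.
- The difference is 33.3 points, 95% CI 3.9 to 51.2. The Miettinen-Nurminen interval is 4.7 to 51.4. Both exclude 0.

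**Step 3: this trial's size**

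About 150 subjects at 1:1:1 gives 150/3 = 50 per arm, and 100 on combined VIS410. The documents give no expected adverse event rates for this trial, so the counts and rates below are assumptions.

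Worked example, 15/50 (30%) against 5/50 (10%): the exact intervals are 17.9 to 44.6% and 3.3 to 21.8%, which overlap. The difference is 20.0 points, Newcombe 95% CI 4.3 to 34.9.

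Full enumeration of both binomials, 50 against 50:

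| True rates (placebo, VIS410) | Exact per-group CIs do not overlap | Newcombe CI of difference excludes 0 |
|---|---|---|
| 10%, 20% | 4.6% | 27.0% |
| 10%, 30% | 31.6% | 72.3% |
| 10%, 40% | 72.7% | 95.3% |
| 10%, 50% | 95.0% | 99.7% |
| 0%, 33% | 99.8% | 100% |

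In counts: with 5, 10, 15 or 20 placebo events out of 50, the difference interval first excludes 0 at 13, 19, 25 or 30 events on VIS410. The exact intervals first separate at 18, 25, 30 or 35. The gap is 5 or 6 events, that is 10 to 12 percentage points.

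Expected width of the missing interval at 10% and 30%: 30.3 points for one dose against placebo (50 and 50), and 24.9 points for combined VIS410 against placebo (100 and 50).

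**The case against.** **SAP 2.3 already states the intent to compare.** It does, and this may be loose drafting rather than a dropped analysis. Even so, the interval it names is for the incidences, which matches 12.1, and it covers only TEAEs. If an interval for the difference was meant, its method and contrasts are still missing.

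**The shells may contain it.** SAP 16.7 says "Table shells are in a separate document", and they were not available, so a difference column cannot be ruled out. But the shells are to be completed after the SAP text is final, and that text does not ask for one.

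**The two documents may rest on different protocol versions.** The SAP cites protocol Version 1.1, and its copy of the assessment schedule lacks the HIV rapid test row found in the protocol. This limits any claim about why the change went undeclared. It does not remove the conflict with the protocol as it stands.

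**The overlap figures test a rule that nobody proposed.** The SAP states no overlap rule and no test, and the gap nearly vanishes for large effects. The table therefore shows how a reader could be misled; it does not describe an error built into the plan. For an estimation-only analysis, the width of the missing interval is the more direct measure. Similarly, VIS-C001 pooled 2 to 50 mg/kg in healthy volunteers, whereas this trial pretreats all subjects to reduce gastrointestinal events. It illustrates the principle and does not forecast this trial.

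**The difference can be derived from the counts.** It can, and the choice of interval makes little difference: for 15/50 against 5/50, Newcombe gives 4.3 to 34.9 and Miettinen-Nurminen 4.5 to 35.4. What is lost is prespecification of the primary estimate, not data.

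**Conclusion.** The concern holds. The protocol says twice that the difference and its 95% CI will be calculated as the primary safety analysis. The SAP text specifies only per-group intervals, and 16.1 is silent. Meanwhile SAP 11.2 does specify between-group tests for viral load and for the proportion virus-negative, which are not primary, so the primary safety comparison is treated less fully than these.

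The consequence is moderate. The endpoint and all counts survive, and a large excess of events would be plain from the per-group intervals. A moderate excess is where the omission matters: at 10% against 30% with 50 per arm, the unreported interval would be about 30 points wide, and a reader relying on overlap would see separation in 32% of trials, against 72% in which the difference interval excludes 0. Those figures rest on assumed rates and 50 per arm; the textual conflict rests on no assumption. It should be fixed before unblinding.

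**What to change.** In SAP 2.3, SAP 12.1 and Table 14.3.1.1, add the risk difference against placebo for 2000 mg, 4000 mg and combined VIS410, with a 95% CI, for AEs, TEAEs, AESIs and SAEs. Name the interval method before unblinding; Newcombe or Miettinen-Nurminen would serve, and the protocol prescribes none. Label the result as the protocol's primary safety analysis, for estimation only. Keep the per-group exact intervals as description. Because SAP 12.1 summarises serious TEAEs, either add an SAE row or state that the two are the same.

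If the sponsor does mean to drop the difference, declare and justify that in SAP 16.1 and bring the protocol into line.

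The cost is SAP wording, extra columns and at most one extra row in one table; no new data are needed. The downside is 4 event types × 3 contrasts = 12 unadjusted intervals, to be read as estimates. That is consistent with SAP 4.1, which makes no multiplicity adjustment.
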